### 11.2 Data Analysis

We will report main trial outcomes by anaemic and non anaemic groups. Continuous data will be presented as mean (95% CI), or median (IQR) if non-normally distributed. Binary data will be presented as frequency (%). Parametric and non parametric variables will be compared using appropriate statistical tests.

Exploratory analyses will utilize the hsTnI profiles to define the optimum method for defining myocardial injury in a subsequent trial, for example maximum values, AUC analyses, and proportions exceeding threshold values. Comparisons across the two study groups will be used to explore the possible validity of this measure in a subsequent large transfusion trigger trial, specifically whether differences exist between patients with different haemoglobin profiles during the perioperative period. Other analyses will explore the relative associations between markers of kidney injury, anaemia, and other factors using regression analysis. We will report the proportion of eligible patients, Hb concentration distribution between groups and mean red blood cell use across groups with 95% confident intervals (CI).

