## 2. Background

### 2.1 Perioperative Blood Transfusion

Epidemiological studies suggest that patient co-morbidities, including anaemia, are associated with increased rates of complications and death following surgery. (5) Anaemia may reflect the severity of chronic disease, and may not have a causative relationship with poor outcomes. Despite this, patients commonly receive blood transfusions to increase haemoglobin concentration with the belief that this may improve clinical outcomes. Some 2.1 million units of red blood cells are transfused each year in the UK, many in the perioperative period, and blood transfusion is an expensive and finite resource. Evidence supports generally restrictive haemoglobin (Hb) transfusion triggers, but the optimum transfusion threshold for important sub-groups of surgical patients remains uncertain.

In the absence of major bleeding, perioperative red blood cell transfusions are typically given to improve oxygen delivery to organs and tissues. Clinicians have particular concern about the risk of myocardial ischaemia, especially among patients with cardiovascular disease. Decision-making is also influenced by potential adverse effects ranging from fluid overload to immune-mediated outcomes, such as increased postoperative infection(6) and tumour recurrence.(7) Published research comparing restrictive and liberal transfusion strategies have typically compared a transfusion threshold of 7-8 g.dL with 9-10 g. dL.(8) Many of these trials excluded patients with co-existing cardiovascular disease (CVD) and those that included this population typically used less restrictive transfusion triggers (usually  $\geq 8\text{g. dL}^{-1}$ ). This reflects concerns over precipitating or exacerbating major adverse cardiac events (MACE) by exposing patients with CVD to anaemia.

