## 9. Subgroups

### 9.1 Anaemia

We will explore cardiac and renal biomarker changes in patients with and without anaemia according to WHO definition and also by current transfusion guidelines. We hope this will inform a study looking at myocardial injury as an endpoint for restrictive versus liberal blood transfusion practice for patients with cardiovascular disease in intensive care. This will enable us to study the range of Troponin values that might occur when the patient becomes eligible for entry to this with a preoperative haemoglobin of 90g/l or less. We will also be able to look at Troponin I levels pre- and post-transfusion. This will not require any further blood samples.

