## 11. Statistics and Data Analysis

### 11.1 Power

We plan to recruit 200 patients. This is an exploratory study, and not based on a formal power calculation. We propose to recruit for fixed period of 12 months to establish recruitment rates, and provide estimates of the values and distribution of clinical outcomes that will be used to design a full trial. On the admission figures quoted above, 600 patients would be eligible for recruitment each year. Assuming a 50% refusal rate, we could realistically expect to recruit 300 (95% Confidence Intervals [CI] 280-320). Planned recruitment of 200 is well within these limits. We expect 50% of participants to be anaemic, based on previous work. (10)

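### Section 11.2 judges troponin for a future transfusion-trigger trial by an anaemic v non-anaemic comparison and names no model of troponin on continuous haemoglobin

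*Combined protocol and SAP*

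**What the plan says.** All references are to the combined protocol and SAP.

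- **Section 11.2, reporting:** "We will report main trial outcomes by anaemic and non anaemic groups".
- **Section 11.2, assessing troponin:** "Comparisons across the two study groups will be used to explore the possible validity of this measure in a subsequent large transfusion trigger trial". The sentence continues: "specifically whether differences exist between patients with different haemoglobin profiles during the perioperative period". Troponin may be summarised by maximum, AUC or the proportion above a threshold. The one regression sentence names kidney-injury markers, anaemia and other factors. No model has troponin as outcome and continuous haemoglobin as predictor.
- **Section 9.1:** biomarker changes will be explored "in patients with and without anaemia according to WHO definition and also by current transfusion guidelines". The section also plans to study the range of troponin at a preoperative haemoglobin of 90 g/L or less, and to look at troponin before and after transfusion.
- **Section 11.1:** "We plan to recruit 200 patients"; "This is an exploratory study, and not based on a formal power calculation"; "We expect 50% of participants to be anaemic, based on previous work".
- **Section 2.1:** "Published research comparing restrictive and liberal transfusion strategies have typically compared a transfusion threshold of" 7–8 with 9–10 g/dL.
- **Sections 4.2.3, 5 and 8:** haemoglobin is recorded preoperatively, at its lowest during surgery, immediately after surgery, as a nadir over the first 7 days from admission, and at transfusion. Section 11.2 does not say which of these defines the groups.

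**The concern.** A haemoglobin profile is continuous and changes over time, so a single binary split is a coarse answer to the question that section 11.2 asks. Two things are at stake.

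The first is precision. Cutting a continuous predictor in two uses less of the data in a cohort of only 200.

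The second is relevance. A group that holds half the cohort mixes mild anaemia with values in the range where triggers are debated. The average difference between the halves does not describe how troponin behaves at 70 compared with 90 g/L. If troponin rises only at low haemoglobin, the mildly anaemic patients dilute the rise. Troponin is the primary endpoint (section 4.2.1), and section 11.1 says the study's estimates will feed the design of a full trial.

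**Working it through.** **The plan's own figure.** The only computed figure in section 11 is expected recruitment of 300 (95% CI 280–320). From 600 eligible and 50% refusal, 600 × 0.5 = 300 and 300 ± 1.96 × √(600 × 0.5 × 0.5) = 276 to 324. The stated limits are close to these, though nearer to a 90% interval (279.9 to 320.1). Nothing below depends on them. No power calculation is given.

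**Inputs.** From section 11.1: N = 200, half anaemic, so about 100 v 100. Assumed for illustration: normal haemoglobin, a linear relation with log troponin, two-sided 5% tests.

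**Information kept by a split.** For a normal predictor cut at quantile q, relative efficiency is φ(z_q)² / [q(1 − q)].

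- q = 0.5: 2/π = 0.637. The loss is 36%, 200 × 0.637 ≈ 127 effective patients, and the interval is 1/√0.637 = 1.25 times as wide.
- 40:60 split: loss 38%. 30:70: loss 42%. 20:80: loss 51%.
- Equal-sized ordered groups: loss 21% with three, 14% with four.

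**Power at a true correlation of 0.20.** This value is chosen because it is about the smallest that a continuous analysis of 200 patients detects with 80% power. Power is Φ(artanh(r)√197 − 1.96).

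- Continuous, linear term: artanh(0.20) × √197 = 2.845, power 81%.
- Two-group split: r falls to 0.20 × √0.637 = 0.160, artanh(0.160) × √197 = 2.26, power 62%. Simulation at r = 0.197 gave 61%.
- Three-knot spline, 2-df test, same linear truth: non-centrality 2.845² = 8.1, power about 72%.

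For 80% power the smallest detectable correlation is about 0.20 with continuous haemoglobin and about 0.24 with the split.

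**Who is in the anaemic group.** The documents give no haemoglobin mean or SD, so these are ranges under assumed normal distributions.

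| Haemoglobin used | Assumed centre, SD (g/L) | At or below 90, of 200 | At 70–100, of 200 |
|---|---|---|---|
| Preoperative | 120–130, 12–20 | about 0–13 | about 1–31 |
| Nadir | 90–105, 12–18 | about 21–100 | about 67–150 |

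On the preoperative assumptions, values of 70–100 g/L make up 1% to 30% of the lower half of the cohort. A troponin shift confined to that range would then appear in the group difference at no more than about 0.30 of its size.

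**Section 9.1 against the question in 11.2.** The guideline classification is another grouping, with no cut-points stated. The range at 90 g/L or less describes one stratum and gives no contrast across levels. Troponin before and after transfusion exists only for transfused patients. None of these gives a fitted troponin value, with an interval, across haemoglobin levels.

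**The case against.** A reader might infer that troponin is related to haemoglobin only through the anaemia split, and that the study therefore cannot show troponin at trigger levels. The documents do not support that. Section 9.1 plans three further looks at troponin, two of which separate low values from mild anaemia and one of which is not a comparison of groups at all. Haemoglobin is collected at several times, so nothing is lost from the data; one comparison uses less of it. The question about haemoglobin profiles also leaves room for more than a binary comparison. These points stand, and they limit the concern to what section 11.2 specifies.

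The size can also be questioned. The 36% needs normality, linearity and a cut at the median. The correlation of 0.20 is illustrative. The 81% belongs to a one-parameter linear model, and a spline gives up about half of the gain. Power for an overall trend is not the same as precision at 70–90 g/L. All of this stands and is carried into the verdict.

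The exploratory label is a weaker defence. It excuses the absence of a power calculation, but not basing the assessment of troponin on a comparison that answers a coarser question than the one posed.

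**Conclusion.** The concern holds as a gap in specification. Section 11.2 rests its assessment of troponin for a trigger trial on an anaemic v non-anaemic comparison, does not name the haemoglobin value that defines the groups, and specifies no model of troponin on continuous haemoglobin. The analyses in section 9.1 are categorical or descriptive and do not fill the gap.

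The split loses about 36% of the information on a linear trend (about 127 effective patients of 200), and more if the groups are unequal. At a correlation of about 0.20 the power is about 61–62% for the split, 72% for a three-knot spline and 81% for a linear term. These figures assume roughly normal haemoglobin and a linear relation. How many patients fall in the trigger range cannot be derived from the documents; it depends heavily on whether preoperative or nadir haemoglobin is used. The flaw is worth correcting but does not invalidate the study, because the data needed are already collected.

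**What to change.** In section 11.2:

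1. Keep the two-group table as description.
2. Make the main troponin–haemoglobin analysis a regression of log TnI on continuous haemoglobin, for example peak postoperative TnI adjusted for preoperative TnI.
3. Name the haemoglobin measure and require it to be taken no later than the troponin sample it is related to. The recovery-room value would qualify for the 24- and 72-hour samples. The unrestricted 7-day nadir would not, since it can fall after both.
4. Use a linear term per 10 g/L, with a three-knot spline to check non-linearity.
5. Adjust for the main confounders in section 11.3.
6. Report fitted TnI ratios with 95% CI at stated haemoglobin levels, with the number of patients near each, only within the observed range.
7. Align section 9.1 with this: state the guideline cut-points and say how its three analyses support the main model.

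The cost is revised wording and one extra model, with no new samples. Intervals at low haemoglobin will be wide and may rest on few patients, which the counts will show. If preoperative haemoglobin is chosen, there may be too few patients at 70–80 g/L to report a fitted value.

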Highly sensitive troponin assays are now available, which allow clinicians to reliably detect cardiac injury in increased numbers of patients who have undergone major surgery. Troponin release after surgery is common, as high as 40% in some studies. Many of these patients do not exhibit classical symptoms and signs of myocardial infarction (MI). Postoperative elevated troponin that does not fulfil standard definitions of MI is referred to as myocardial injury after non-cardiac surgery (MINS). Potential mechanisms for MINS are coronary events due to plaque rupture or coronary artery thrombosis, oxygen supply-demand imbalance or troponin leak resulting from inflammation.

Acute kidney injury (AKI) is also a leading cause of morbidity and mortality following major surgery with an estimated incidence of 10% in undergoing orthopedic surgery. Epidemiological work has identified anaemia as a risk factor for postoperative acute kidney injury (AKI).

Patients undergoing surgery for fractured neck of femur are often elderly, with co-morbidities and a high risk of postoperative complications, including MI and AKI. We propose to conduct a study with the following aims:

1. To describe the incidence of anaemia and transfusion in patients undergoing surgery for fractured neck of femur.
2. To use clinical and biochemical data to measure the incidence of perioperative cardiac and kidney injury in this group.
3. To evaluate highly sensitive serum troponin and urinary MALDI-MS as possible endpoints in a future prospective randomised trial of perioperative transfusion.

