## **3 Study Objectives and Experimental Design**

### **3.1 Study Objectives**

The objectives of this study is threefold:

1. to measure the incidence of perioperative anaemia and transfusion in patients undergoing surgery for fractured neck of femur.
2. to understand the changes that occur over time in the level of Troponin I in patients undergoing surgery for fractured neck of femur and to answer whether Troponin I can be used in these patients as a real-time marker of myocardial injury. We hope that this will validate the use of Troponin I as the endpoint for a future trial looking at the impact of liberal vs restrictive perioperative blood transfusion in this patient group.
3. to measure the incidence of acute kidney injury in patients undergoing surgery for fractured neck of femur and to evaluate the performance of MALDI-MS against conventional tests of renal function.

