#### 4.1.2 Secondary Objectives

- To estimate the rate of acute kidney injury using Acute Kidney Injury Network (AKIN) Classification, Serum Creatinine and Urinary MALDI-MS.
- To observe whether changes in Troponin I levels are reflected by electrocardiographic changes via an ECG taken on the 3rd postoperative day.
- To define the clinical diagnosis rate of myocardial infarction according to universal definitions
- To observe rate of transfusion and transfusion trigger
- To estimate the incidence of postoperative complications, in particular infectious complications and delirium.
- To measure hospital length of stay
- To measure 30-day, 90-day and hospital mortality.
- To measure economic and quality of life outcomes

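### The plan sets out to evaluate the performance of MALDI-MS, but the analyses stated for kidney markers do not report discrimination or accuracy

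*Combined protocol and SAP*

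**What the plan says.** **Objectives.** The third of the three objectives in section 3.1 includes a commitment "to evaluate the performance of MALDI-MS against conventional tests of renal function". The third aim in section 1.1 is related but different: "To evaluate highly sensitive serum troponin and urinary MALDI-MS as possible endpoints in a future prospective randomised trial of perioperative transfusion". Section 4.1.2 words the kidney objective more narrowly: "To estimate the rate of acute kidney injury using Acute Kidney Injury Network (AKIN) Classification, Serum Creatinine and Urinary MALDI-MS". It does not mention performance.

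**Analysis.** Section 11.2 starts from a general rule: "We will report main trial outcomes by anaemic and non anaemic groups". Its only further statement about kidney markers is "Other analyses will explore the relative associations between markers of kidney injury, anaemia, and other factors using regression analysis". The same section does list candidate summaries, "for example maximum values, AUC analyses, and proportions exceeding threshold values", but these are for the hsTnI profiles. Sections 3.2 and 9.1 add comparisons of renal injury and renal biomarkers by anaemia status.

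**AKI definition.** The outcome list in section 3.2 uses KDIGO stage and section 4.1.2 uses AKIN. The staging table in Appendix D names no system.

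**Sampling.** Sections 3.2 and 5 plan blood samples before surgery and at 24 and 72 hours, and urine within 24 hours and at 4 to 6 days after surgery. Section 8 also lists a preoperative urinary MALDI-MS measurement, which sections 3.2 and 5 do not.

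**The concern.** Performance of one test against another means how well it classifies patients, or how closely it agrees, relative to a reference. The plan names no measure of this for MALDI-MS: no sensitivity, specificity, predictive value, ROC AUC or agreement statistic, and no threshold for a positive result. The comparisons by anaemia group answer a different question, because they split patients by haemoglobin and not by AKI status. A regression reported as associations shows that two quantities move together, but not how many injured patients the test finds or how many uninjured patients it flags.

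This leaves one of three stated objectives without an estimate. It also leaves choices open until after the data are seen. There are two postoperative urine samples, more than one AKI definition and no stated cut-off. With few AKI cases, choosing the best-looking combination afterwards would give optimistic accuracy figures.

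**Working it through.** **1. Is there a figure in the plan to reproduce?** No. Section 11.1 gives a target of 200 patients and says it does not rest on a formal power calculation. No precision is stated for MALDI-MS. The check is therefore one of logic, followed by the precision that an accuracy analysis would have.

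**2. Does an association determine performance?** For a test read as positive or negative,

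OR = [sens / (1 − sens)] × [spec / (1 − spec)].

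An odds ratio of 9 arises from each of these pairs:

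| Sensitivity | Specificity | Calculation |
|---|---|---|
| 0.32 | 0.95 | 0.474 × 19 = 9 |
| 0.50 | 0.90 | 1 × 9 = 9 |
| 0.75 | 0.75 | 3 × 3 = 9 |
| 0.90 | 0.50 | 9 × 1 = 9 |

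(The first sensitivity is 0.321 before rounding.) These are four very different tests, and the coefficient alone does not tell them apart.

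**3. How many AKI cases can be expected?** Section 1.1 gives "an estimated incidence of 10% in undergoing orthopedic surgery". With N = 200 (section 11.1), cases = 200 × 0.10 = 20 and non-cases = 180. The 10% refers to orthopaedic surgery in general, while the same section describes hip-fracture patients as at high risk of complications including AKI. As an assumed upper scenario, 20% gives 40 cases and 160 non-cases.

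**4. Precision of sensitivity and specificity.** Exact (Clopper-Pearson) 95% limits for x out of n are the 0.025 quantile of Beta(x, n − x + 1) and the 0.975 quantile of Beta(x + 1, n − x). Both true values are assumed to be 0.80.

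| Incidence | Sensitivity, 95% CI | Specificity, 95% CI |
|---|---|---|
| 10% (protocol) | 16/20: 0.563 to 0.943 | 144/180: 0.734 to 0.856 |
| 20% (assumed) | 32/40: 0.644 to 0.909 | 128/160: 0.730 to 0.859 |

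**5. Precision of the ROC AUC (A).** Hanley-McNeil: SE² = [A(1 − A) + (n₁ − 1)(Q₁ − A²) + (n₀ − 1)(Q₂ − A²)] / (n₁n₀), with Q₁ = A/(2 − A) and Q₂ = 2A²/(1 + A).

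For an assumed A = 0.75 with n₁ = 20 and n₀ = 180:
- Q₁ = 0.600, Q₂ = 0.643, A² = 0.5625.
- Numerator = 0.1875 + 19 × 0.0375 + 179 × 0.0804 = 15.28.
- SE = √(15.28 / 3600) = 0.065, and the half-width is 1.96 × 0.065 ≈ 0.13.

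For other assumed values with 20 cases, the 95% CI is 0.57 to 0.83 at A = 0.70, 0.68 to 0.92 at 0.80, and 0.81 to 0.99 at 0.90. With 40 cases and A = 0.80 it is 0.71 to 0.89.

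**6. Do the samples support such an analysis?** Yes, for the first postoperative urine sample. It is taken within 24 hours, and the preoperative, 24-hour and 72-hour creatinine values can define AKI around and after it. The second urine sample, at 4 to 6 days, falls after the last planned creatinine sample, although section 5 says that routine blood results will also be recorded.

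**The case against.** The study is declared exploratory, MALDI-MS is a secondary endpoint, and section 4.1.2 asks only for an AKI rate. The regression sentence is broad enough to include MALDI-MS against creatinine. All of this is fair, and it limits the weight of the point. It does not remove it: being exploratory explains the absence of a power calculation, but section 3.1 still states a performance objective and no section says which quantity will answer it.

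Three stronger readings are tempting, and the documents do not support them.

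- *A regression cannot yield diagnostic performance.* A logistic model of AKI on MALDI-MS gives predicted risks, and from these a c-statistic or ROC curve. The accurate statement is that section 11.2 neither names AKI status as the outcome nor says that discrimination will be reported.
- *About 20 AKI cases are too few for a regression with several covariates.* This presupposes a logistic model with binary AKI as the outcome, which the plan does not state. Section 4.2.2 lists serum creatinine and urinary MALDI-MS as endpoints. A linear model of creatinine would use all patients with data, up to 200. No limit on covariates follows from the text.
- *Without accuracy measures the study could not judge MALDI-MS as an endpoint for a future trial.* Sections 11.1 and 11.2 plan estimates of values, distributions and differences by anaemia group, and these bear on that aim. Section 2.4 also notes that creatinine rises late, so accuracy against creatinine-defined AKI would not settle endpoint suitability on its own.

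**Conclusion.** The point holds as a mismatch between an objective and its analysis. Followed as written, section 11.2 would deliver summaries by anaemia group and associations, and would leave the performance objective in section 3.1 without a reported estimate. The supporting definitions (AKI system and time window, index urine sample, cut-off) are also not fixed.

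The remedy is feasible with samples already planned, but its precision is modest. With about 20 cases, the interval for sensitivity spans nearly 40 percentage points (0.943 − 0.563 = 0.38) and the AUC has a half-width of about 0.13. With about 40 cases the sensitivity interval narrows to about 27 points (0.909 − 0.644 = 0.265).

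These figures rest on the protocol's N = 200 and 10% incidence, and on assumed values for the 20% scenario, for sensitivity and specificity (0.80) and for the AUC. They also take all 200 patients to have usable urine and creatinine, so missing samples would widen the intervals. The change should be made before analysis. The primary troponin analysis is not affected.

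**What to change.** In section 11.2, add a short paragraph for the MALDI-MS objective that states:

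1. **Index test:** MALDI-MS in the postoperative urine sample taken within 24 hours. Say how the 4-to-6-day sample and the preoperative sample listed only in section 8 will be used.
2. **Reference:** one named creatinine-based AKI definition, reconciling KDIGO (section 3.2) with AKIN (section 4.1.2) and labelling Appendix D to match, over a stated window covered by the 24-hour and 72-hour creatinine samples.
3. **Measures:** ROC AUC with 95% CI, and sensitivity and specificity with exact 95% CIs at a pre-stated cut-off. If the cut-off is derived from the study data, say so and correct for optimism.
4. **Expected precision:** about 20 cases at 10% incidence and about 40 at an assumed 20%, with the intervals shown in the working.
5. **Regression:** keep it as a secondary analysis.

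Also reconcile section 4.1.2, which asks only for the AKI rate, with the performance objective in section 3.1.

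The cost is some wording and a little more analysis, with no additional patients or samples. The drawback is that the stated precision will look modest.
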